16.6 MANAGEMENT OF QTc PROLONGATION

For a list of medications known to prolong QTc, please see Appendix 8.

The electrocardiogram (ECG) must be evaluated by the local cardiologist or Investigator or qualified personnel at site, for the presence of QTcB prolongation or other abnormalities, in particular any changes in the T Wave morphology that would suggest a higher likelihood for the development of any arrhythmia.

Any clinically significant abnormal findings of QTcB prolongations will be recorded as adverse events.

On study monitoring

For a single QTcB value >480ms, withhold vandetanib (and selumetinib if in combination phase).

[figure not shown]
ECGs will be followed at least once a week (performed on the same day each week) along with electrolytes, until QTcB falls below 480ms. Vandetanib may then be resumed at a permanently lower dose (dosing every other day at same dose level), after the QTcB returns to <480ms.

If vandetanib is restarted after the QTcB prolongation has resolved, ECGs (along with electrolytes) should be performed two weeks following restarting study treatment and then prior to Day 1 of each cycle thereafter.

Serum potassium levels should be maintained at 4.0mmol/L or higher and serum magnesium and calcium should be kept within normal range to reduce the risk of QTc prolongation.

Vandetanib treatment may be resumed at a lower dose after the QTcB recovers to less than 480 ms.

16.7 INVESTIGATION OF ASYMPTOMATIC DECREASES IN LVEF.

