5.4.2 Dose reductions

This section is applicable to both the dose escalation phase and also the expansion cohort.

The dose of the combination treatment will be reduced to the previous dose level for any patient who experiences a DLT. If a patient has a dose reduction, their dose should not be re-escalated. NCI CTCAE Version 4.02 is applicable for Section 5.4.2.

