5.4.2.1 Vandetanib and Selumetinib dose reduction

During single agent (vandetanib) phase

If vandetanib administration is interrupted during the single agent phase at the start of Cycle 1 (first 14 days):

- If the interruption was unrelated to vandetanib, administration can recommence as per protocol with no dose reduction.
- If the interruption was related to vandetanib,
 - If toxicity \leq G2, administration can continue as per protocol with no dose reduction on return to Grade 1 or baseline.
 - If toxicity is Grade 3 or above the patient must permanently discontinue study treatment.

During combination phase

If combination treatment is interrupted for **<10 days** during the combination treatment, on re-starting treatment:

- If the interruption was **unrelated to vandetanib or selumetinib**, both drugs can be administered together in combination following the interruption with no dose reduction.
- If the interruption was **related to vandetanib**, on return to Grade 1 or below, vandetanib should be dose reduced to the next lowest dose level od*. A dose reduction to selumetinib is not mandated.

*If single agent dose is 100mg then administration of vandetanib given every other day can be considered however selumetinib must also be administered in combination (selumetinib is not to be administered as a single agent).

- If the interruption was related to selumetinib, on return to Grade 1 or below, selumetinib should be dose reduced to next lowest dose level. A dose reduction to vandetanib is not mandated.

If combination treatment is interrupted for 10-14 days, on re-starting treatment:

- If the interruption was unrelated to vandetanib or selumetinib, vandetanib should be administered as a single agent (no dose reduction) for 10 days at steady state dose level (dependant on cohort) before re-introducing selumetinib (no dose reduction).
- If the interruption was related to vandetanib, vandetanib should be administered as a single agent for 10 days at the next lowest dose level od* before re-introducing selumetinib. A dose reduction to selumetinib is not mandated.
*If single agent dose is 100mg then administration of vandetanib given every other day can be considered however following re-loading, selumetinib must also be administered in combination with vandetanib every other day (selumetinib is not to be administered as a single agent).

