- If the interruption was related to selumetinib, vandetanib should be administered as a single agent for 10 days at the same dose level od (no dose reduction) before re-introducing selumetinib at the next lowest dose level.

Administration of vandetanib given every other day can be considered following a dose interruption however selumetinib must also be administered in combination.

Selumetinib must not be administered as a single agent.

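### Single-agent phase: after QTcB above 480 ms Appendix 16.6 restarts vandetanib at half dose, while Section 5.4.2.1 allows full dose at Grade 2 or below

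*Protocol*

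**What the plan says.** **Appendix 16.6 (QTc management).** The trigger covers both phases: "For a single QTcB value >480ms, withhold vandetanib (and selumetinib if in combination phase". The bracket shows that the rule also applies when vandetanib is given alone. Two sentences then deal with restart. The first is "Vandetanib may then be resumed at a permanently lower dose (dosing every other day at same dose level), after the QTcB returns to <480ms". The second, at the end of the appendix, is "Vandetanib treatment may be resumed at a lower dose after the QTcB recovers to less than 480 ms". Both make a lower dose the term of restart, and the first says what that dose is.

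**Section 5.4.2.1, single-agent phase (first 14 days of Cycle 1).** If the interruption is unrelated to vandetanib, there is no reduction. If it is related and the toxicity is Grade 2 or below, "administration can continue as per protocol with no dose reduction on return to Grade 1 or baseline". If it is related and higher, "If toxicity is Grade 3 or above the patient must permanently discontinue study treatment".

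**Section 5.4.2.1, combination phase.** For a vandetanib-related interruption under 10 days, "vandetanib should be dose reduced to the next lowest dose level od", with every-other-day dosing as an option at 100 mg. A general sentence adds: "Administration of vandetanib given every other day can be considered following a dose interruption however selumetinib must also be administered in combination".

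**The link between them.** Section 5.4.1.1 lists the QTc appendix among guidelines for managing other toxicities. It sets no order of precedence.

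**The concern.** A patient in the first 14 days can have a QTcB above 480 ms that is attributed to vandetanib and graded 2 or below. After recovery, two parts of the same protocol give different restart doses. The appendix halves the dose for good; the body text allows it to continue unchanged.

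The protocol's own background explains why this matters. Section 2.2.1.5 reports that QTc prolongation on vandetanib was handled by interrupting and then reducing the dose, and it describes the events as dose-dependent. Section 2.2.1.4 gives a half-life of about 10 to 19 days, so an unreduced restart is not quickly undone. The phase also includes a four-day 300 mg loading period, and Section 7.2.1.2 schedules an ECG for every patient at Day 5 (+/- 1 day), so the protocol looks for this event at that time.

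**Working it through.** The plan gives no figure to reproduce. The check is a comparison of the rules, followed by dose arithmetic.

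**Step 1. Which rules reach the case?** The case is QTcB above 480 ms, single-agent phase, vandetanib-related, Grade 2 or below.

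| Rule | Reaches the case? | Vandetanib at restart |
|---|---|---|
| Appendix 16.6, first restart sentence | Yes, both phases | Same level, every other day, permanently |
| Appendix 16.6, second restart sentence | Yes, both phases | A lower dose, not specified |
| 5.4.2.1, single-agent, Grade 2 or below | Yes | No reduction |
| 5.4.2.1, every-other-day options | No, selumetinib must be given too | Not applicable |

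The two rules that name a dose for this case give different doses. The every-other-day wording in 5.4.2.1 does not bridge them, because it is tied to giving selumetinib in combination.

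**Step 2. Size of the difference.** Inputs: the 100 mg once-daily dose of Cohorts 1-3 (Section 3.2.1), and the 200 and 300 mg doses that Section 5.1.1 says will be considered. Restart is assumed to be at the once-daily maintenance dose, after loading.

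Average daily dose under 5.4.2.1 = dose; under 16.6 = dose / 2.

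- 100 mg: 100 versus 100/2 = 50 mg/day
- 200 mg: 200 versus 200/2 = 100 mg/day
- 300 mg: 300 versus 300/2 = 150 mg/day

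The ratio is 2.0 at each level. Only the 100 mg row is a planned starting regimen. If carried through the 28 combination days of Cycle 1, it is 28 x 100 = 2,800 mg against 14 x 100 = 1,400 mg.

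**Step 3. How many patients?** Section 2.2.1.5 gives QTc prolongation in under about 2% at 100 mg (with chemotherapy) and about 5% to 10% at 300 mg. If those rates carried over:

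- dose escalation at 100 mg: under 42 x 0.02 = 0.84 to 50 x 0.02 = 1.0 patients
- expansion at 100 mg: under 30 x 0.02 = 0.6 patients
- expansion at 300 mg: 30 x 0.05 = 1.5 to 30 x 0.10 = 3 patients

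These counts cover all QTc prolongation in both phases. The share falling in the first 14 days at Grade 2 or below is not given and can only be smaller than the total. The rates come from other regimens without this loading schedule, so the counts are a rough guide.

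**The case against.** **The specific rule governs.** Appendix 16.6 is specific to QTc and is cited from within Section 5.4. Section 5.4.2.1 is general and only permits continuation as the protocol provides, and the appendix is part of the protocol. A careful site would use the lower dose and breach nothing. That much stands, and it keeps the point minor. It does not remove the conflict: 16.6 is specific by toxicity, 5.4.2.1 is specific by phase, and the same clause that permits continuation also says that the dose is not reduced. A site restarting at full dose could say that it followed the text.

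**A figure in Appendix 16.6 is not shown.** It may add instructions. Nothing here rests on what it contains or lacks; the two running texts disagree whatever it shows.

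**Two stronger readings are tempting and are not supported.**

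- *The dose limiting toxicity step-down leaves vandetanib unreduced.* QTc above 500 msec is a dose limiting toxicity (Section 3.1.1), and Section 5.4.2 says "The dose of the combination treatment will be reduced to the previous dose level for any patient who experiences a DLT". Since Cohorts 1-3 all use vandetanib 100 mg once daily, a reader might infer that only selumetinib falls (150 to 100 mg/day from Cohort 3, 100 to 50 mg/day from Cohort 2). But such a value is also above 480 ms, so 16.6 withholds both drugs. That interrupts the combination, and 5.4.2.1 then reduces vandetanib if the event is related to it, with every-other-day dosing available at 100 mg. The rules can be applied together, and both of these reduce vandetanib.
- *At Grade 3 or above in the single-agent phase the two texts contradict each other.* Section 5.4.2.1 says the patient must stop; 16.6 says vandetanib may resume. A mandatory rule limits a permissive one, so a site reading both would stop. A cross-reference would help, but this is not a contradiction.

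**Conclusion.** Wrong as written, minor. In the single-agent phase, for a vandetanib-related QTcB above 480 ms of Grade 2 or below, Appendix 16.6 and Section 5.4.2.1 give restart doses that differ two-fold, 50 against 100 mg/day at the planned dose, with no stated precedence.

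This assumes that some QTcB values above 480 ms are graded 2 or below. The grading table is not reproduced in the protocol. Appendix 16.6 itself provides for restart in either phase, which would have no use in this phase for vandetanib-related events if every such value required permanent discontinuation.

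Few patients would be affected. The withholding rule itself is clear, and no sample size, power or estimate depends on the point. It matters as a safety instruction that two sites could carry out differently while each following the protocol.

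**What to change.** In Section 5.4.2.1, add to the single-agent branch for Grade 2 or below: *except QTcB >480 ms, for which vandetanib is restarted only at the reduced dose in Appendix 16.6*.

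In Appendix 16.6, add a cross-reference to the 5.4.2.1 rule that vandetanib-related toxicity of Grade 3 or above in the single-agent phase means permanent discontinuation.

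The cost is protocol wording in two places. No procedures, visits or patients are added, and the step-down in Section 5.4.2 need not change.

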16.8 MEDICATIONS KNOWN TO PROLONG THE QT INTERVAL AND/OR INDUCE TORSADES DE POINTES

Concomitant use of medications generally accepted as having a risk of causing Torsades de Pointes (Table 1) are not allowed within 2 weeks of first dose or during study (at least 4 weeks for Levomethadyl). These drugs should also be avoided for up to 4 weeks following discontinuation of study treatment.

If after reviewing the list of drugs in Table 1, the investigator finds that any ongoing patient is now taking a Group 1 drug, the investigator is to manage the patient immediately as follows:

- The investigator should switch the patient to an alternative drug as soon as possible.
- If it is not possible to switch the patient to an alternative drug, the patient will have to stop study treatment.

Table 1 Group 1 Drugs

Drug (Generic Names)	Drug Class (Clinical Usage)	Comments
Amiodarone	Anti-arrhythmic / abnormal heart rhythm	TdP risk regarded as low
Arsenic trioxide	Anti-cancer / Leukemia	
Astemizole	Antihistamine / Allergic rhinitis	No Longer available in U.S.
Bepridil	Anti-anginal / heart pain	
Chloroquine	Anti-malarial / malaria infection	
Chlorpromazine	Anti-psychotic/ Anti-emetic / schizophrenia/ nausea	
Cisapride	GI stimulant / heartburn	Restricted availability
Clarithromycin	Antibiotic / bacterial infection	
Disopyramide	Anti-arrhythmic / abnormal heart rhythm	
Dofetilide	Anti-arrhythmic / abnormal heart rhythm	
Domperidone	Anti-nausea / nausea	Not available in the U.S.
Droperidol	Sedative; Anti-nausea / anesthesia adjunct, nausea	
Erythromycin	Antibiotic; GI stimulant / bacterial infection; increase GI motility	
Halofantrine	Anti-malarial / malaria infection	
Haloperidol	Anti-psychotic / schizophrenia, agitation	When given intravenously or at higher-than- recommended doses, risk of sudden death, QT prolongation and torsades increases.
Ibutilide	Anti-arrhythmic / abnormal heart rhythm	
Levomethadyl	Opiate agonist / pain control, narcotic dependence	

CONFIDENTIAL**Table 1 Group 1 Drugs**

Drug (Generic Names)	Drug Class (Clinical Usage)	Comments
Mesoridazine	Anti-psychotic / schizophrenia	
Methadone	Opiate agonist / pain control, narcotic dependence	
Moxifloxacin	Antibiotic / bacterial infection	
Pentamidine	Anti-infective / pneumocystis pneumonia	
Pimozide	Anti-psychotic / Tourette's tics	
Probucol	Antilipemic / Hypercholesterolemia	No longer available in U.S.
Procainamide	Anti-arrhythmic / abnormal heart rhythm	
Quinidine	Anti-arrhythmic / abnormal heart rhythm	
Sotalol	Anti-arrhythmic / abnormal heart rhythm	
Sparfloxacin	Antibiotic / bacterial infection	
Terfenadine	Antihistamine / Allergic rhinitis	No longer available in U.S.
Thioridazine	Anti-psychotic / schizophrenia	
Vandetanib (*Does not apply to this study)	Anti-cancer / Thyroid cancer	"Zactima®" is the proposed brand name

Table 2: Drugs that in some reports may be associated with Torsades de Pointes but at this time lack substantial evidence of causing Torsades de Pointes.

Co-administration of drugs that in some reports might be associated with TdP but at this time lack substantial evidence (Table 2) should be avoided within 2 weeks of first dose and during study. However, these drugs will be allowed, at the discretion of the Investigator, if considered absolutely necessary. In such cases, the subject must be closely monitored including regular checks of QTc and electrolytes. For patients who start on the drugs in this group while on the study treatment, the ECG must be checked within 24 hours of commencing the concomitant medication and then at least once per week while the patient remains on the medication. The frequency of ECG monitoring could revert to the standard schedule if no QTc prolongation has been noted during 4 weeks of co-administration of a drug from Table 2. The electrolytes should be maintained within the normal range using supplements if necessary.

CONFIDENTIAL**Table 2 Group 2 Drugs**

Drug (Brand Names)	Drug Class (Clinical Usage)	Comments
Alfuzosin	Alpha1-blocker / Benign prostatic hyperplasia	
Amantadine	Dopaminergic/Anti-viral / Anti-infective/ Parkinson's Disease	
Atazanavir	Protease inhibitor / HIV	
Azithromycin	Antibiotic / bacterial infection	
Chloral hydrate	Sedative / sedation/ insomnia	
Clozapine	Anti-psychotic / schizophrenia	
Dolasetron	Anti-nausea / nausea, vomiting	
Dronedarone	Anti-arrhythmic / Atrial Fibrillation	
Escitalopram	Anti-depressant / Major depression/ Anxiety disorders	
Famotidine	H2-receptor antagonist / Peptic ulcer/ GERD	
Felbamate	Anti-convulsant / seizure	
Flecainide	Anti-arrhythmic / abnormal heart rhythm	
Foscarnet	Anti-viral / HIV infection	
Fosphenytoin	Anti-convulsant / seizure	
Gatifloxacin	Antibiotic / bacterial infection	
Gemifloxacin	Antibiotic / bacterial infection	
Granisetron	Anti-nausea / nausea and vomiting	
Indapamide	Diuretic / stimulate urine & salt loss	
Isradipine	Anti-hypertensive / high blood pressure	
Lapatinib	Anti-cancer / breast cancer, metastatic	
Levofloxacin	Antibiotic / bacterial infection	
Lithium	Anti-mania / bipolar disorder	
Moexipril/HCTZ	Anti-hypertensive / high blood pressure	
Nicardipine	Anti-hypertensive / high blood pressure	
Nilotinib	Anti-cancer / Leukemia	
Octreotide	Endocrine / acromegaly, carcinoid diarrhea	
Ofloxacin	Antibiotic / bacterial infection	
Ondansetron	Anti-emetic / nausea and vomiting	
Oxytocin	Oxytocic / Labor stimulation	
Paliperidone	Antipsychotic, atypical / Schizophrenia	

CONFIDENTIAL**Table 2 Group 2 Drugs**

Drug (Brand Names)	Drug Class (Clinical Usage)	Comments
Perflutren lipid microspheres	Imaging contrast agent / Echocardiography	
Quetiapine	Anti-psychotic / schizophrenia	
Ranolazine	Anti-anginal / chronic angina	
Risperidone	Anti-psychotic / schizophrenia	
Roxithromycin*	Antibiotic / bacterial infection	*not available in the United States
Sertindole	Antipsychotic, atypical / Anxiety, Schizophrenia	
Sunitinib	Anti-cancer / RCC, GIST	
Tacrolimus	Immunosuppressant / Immune suppression	
Tamoxifen	Anti-cancer / breast cancer	
Telithromycin	Antibiotic / bacterial infection	
Tizanidine	Muscle relaxant /	
Vardenafil	phosphodiesterase inhibitor / vasodilator	
Venlafaxine	Anti-depressant / depression	
Voriconazole	Anti-fungal / anti-fungal	
Ziprasidone	Anti-psychotic (schizophrenia)
